HIV Testing Services Program Officer
Ministry of Health, Dept of HIV/AIDS
Lilongwe, Malawi
Tele: [name]
Email: [contact]

[name]
Research Coordinator
Partners in Hope
[name], Lilongwe, Malawi

Use of HIV Self-Test Kits to Increase Identification of HIV-Infected Individuals and Their Partners

SCHEMA

Purpose: To evaluate the feasibility and cost-effectiveness of self-testing strategies within health facilities compared to standard of care in the following settings:
(1) group self-testing in outpatient departments (OPD) and sexually transmitted infection (STI) clinics compared to standard of care and optimized standard of care HIV testing and counseling; and
(2) self-testing for partners of HIV+ index clients compared to standard of care and optimized standard of care partner notification strategies.

Design: Unblinded cluster-randomized controlled trial

Study Population: Aim 1: Individuals 15 years of age and older not already known to be HIV-positive
Aim 2: HIV-positive individuals 15 years of age and older with at least one sexual partner with unknown HIV status

Sample Size: **Aim 1: 15 clusters with a total of 15,000 participants (5,000 per arm, 1,000 per site)**
Aim 2: 15 clusters with a total of 7,500 participants (2,500 per arm, 500 per site)

Intervention: Aim 1: To test the feasibility and cost-effectiveness of group HIV self-testing in outpatient department (OPD) and sexually transmitted infections (STI) clinics

- Arm 1: Standard of care for provider-initiated testing and counseling (PITC)
- Arm 2: Optimized standard of care for PITC
- Arm 3: Group HIV self-testing

Aim 2: To test the feasibility and cost-effectiveness of partner HIV self-testing

- Arm 1: Standard of care for partner testing
- Arm 2: Optimized standard of care for partner testing
- Arm 3: HIV self-testing

Study Duration: Approximately 18 months total

Aim 1: To test the feasibility and cost-effectiveness of group HIV self-testing for patients in waiting areas of outpatient department (OPD) and sexually transmitted infections (STI) clinics

Primary Objectives:

- To determine whether group self-testing in waiting areas of OPD and sexually transmitted STI clinics is superior in regard to number of individuals HIV tested compared to optimized standard of care (provider-initiated testing and counseling; PITC)
- To determine whether group self-testing in waiting areas of OPD and STI clinics is cost-effective compared to optimized standard of care using PITC

Secondary Objectives:

- To assess the acceptability of self-testing in waiting areas of OPD and STI clinics

- To determine whether group self-testing in waiting areas of OPD and STI clinics is superior in regard to number of HIV+ individuals identified (testing yield)
- To determine whether group self-testing in waiting areas of OPD and STI clinics is superior in regard to linkage rates for those who identify as HIV-positive compared to standard of care and optimized standard of care (PITC)

Aim 2: To evaluate the feasibility and cost-effectiveness of self-testing for partners

Primary Objectives:

- To determine whether providing index clients with HIV self-test kits for partners results in a greater number of partners tested as compared to optimized standard of care for partner notification and testing (referral slip)
- To determine whether providing index partners with HIV self-test kits is cost-effective compared to optimized standard of care using referral slips

Secondary Objectives:

- To assess the acceptability of giving self-test kits to index clients for partner testing
- To determine whether providing index partners with HIV self-test kits is superior to optimized standard of care in regard to identifying HIV+ partners (yield of testing)
- To determine whether providing index partners with HIV self-test kits is superior to optimized standard of care in regard to linkage rates among those who identify as HIV-positive
- To determine whether providing self-test kits to index clients and their partner is superior to optimized standard of care in regard to partner disclosure by the index client

1 INTRODUCTION

1. BACKGROUND

Despite increased access to HIV services, use of HIV testing in sub-Saharan Africa remains low. In Malawi, only 42% of the adult population received an HIV test in the last year.¹ Men are less likely to test than women (82% of women have ever tested in their lifetime compared to 70% of men).¹ In order to reach the UN 90-90-90 goals, innovative solutions must be approached to identify and test individuals living with HIV. Two initiatives promise to increase testing and yield: Provider Initiated Testing and Counseling and Partner Notification Services.

Provider initiated testing increases the ability to test people who are already attending health services and are either unwilling or unable to independently seek an HIV test.^{2,3} The strategy is prioritized for high-risk clients (ANC, OPD, STI, and TB clients) and is an efficient and cost-effective way to identify new HIV cases among these groups.⁴ However, PITC is rarely implemented in routine care.⁵⁻⁸ Furthermore, men are still underrepresented in PITC efforts.^{4,9}

Partner Notification Services, also known as Contact Tracing, have also been identified to augment HIV case finding.^{10,11} The feasibility and effectiveness of Partner Notification Services in Sub-Saharan African countries has been demonstrated with much success.¹²⁻¹⁶ Within study settings in Malawi and Cameroon, active partner notification was effective with high rates of partner testing, 51% and 66.8% respectively, and positivity rates between 50-64%.^{13,14}

Partner notification services have the potential for high impact in new case identification as the rate of HIV cases among partners has been shown to be tenfold higher than the national prevalence.^{10,13,14} Early case identification is also key in preventing late stage patient presentation with high morbidity and less efficacious treatment outcomes. The case finding effectiveness of Partner Notification Services can result in earlier diagnosis of individuals, earlier initiation of ART, and prevention of HIV transmission. However, men are being missed in Partner Notification Services, limiting the strategy's impact. The percent return rates of men during passive referral is half that seen by women partners.¹⁴ Strategies to improve testing of men are needed.

Prior Research on Self-Testing

A recently introduced method of HIV self-test screening within Malawi has shown high testing uptake among men. A study piloting the use of HIV self-testing demonstrated high uptake in adolescent men (89.3% in men aged 16-19 years of age) with rates remaining as high as 60% among men up to age 39 (compared to only 42% of the general male population who have been tested in the previous year).^{1,17} Self-test screening also promotes partner testing and can be used to facilitate status disclosure.^{18,19}

Overall, feasibility and uptake of self-test screening has been successfully demonstrated within Malawi allowing self-test screening to serve as a new key tool in increasing access to testing.^{17,18,20,21,22} HIV self-test screening has been shown to be accurate, safe, and cost/quality of life analysis has also demonstrated its usefulness.^{17,18,20, 22-25} However, self-test kits have been primarily distributed in community settings outside the standard health care system. To date, self-test kits have not been distributed within health facilities nor studied for partner testing. Combining self-testing with existing health systems may improve the scalability of self-test kits at a national level.

This study compliments the existing STAR study conducted in Malawi and elsewhere. STAR focuses primarily on non facility-based distribution, such as communities and schools. We examine self-test integration for routine health services, addressing a gap in self-test knowledge.

2. RATIONALE

While self-testing and partner notification strategies have been studied separately, these strategies have never been examined jointly as a means to improve partner disclosure and testing. Furthermore, self-test kits have not been piloted within existing health systems, limiting the feasibility of self-test kits outside study settings.

We propose to study the role of self-testing in identifying HIV-positive individuals and to determine whether self-test kits can be given to index clients as a means to facilitate partner disclosure and partner testing.

3. HYPOTHESES

- Aim 1: Group self-testing will (1) increase the number of OPD and STI clients tested for HIV, (2) increase HIV testing yield, and (3) be cost-effective compared to the optimized standard of care
- Aim 2: Self-test kits given to index clients will (1) increase the number of index partners who test for HIV; (2) increase yield of partner testing, and (3) be cost-effective compared to the optimized standard of care for partner notification and testing, and will (4) increase partner disclosure by the index client

2. AIM 1: GROUP SELF-TESTING

2.1. OBJECTIVES

2.1.1. Primary Objectives:

- To determine whether group self-testing in waiting areas of outpatient departments (OPD) and sexually transmitted infection (STI) clinics is superior in regard to number tested compared to optimized standard of care (provider-initiated-testing-and-counseling; PITC)
- To determine whether group self-testing in waiting areas of OPD and STI clinics is cost-effective compared to optimized standard of care using PITC

2.1.2. Secondary Objectives:

- To assess the acceptability of self-testing in waiting areas of OPD and STI clinics
- To determine whether group self-testing in waiting areas of OPD and STI clinics is superior in regard to number of HIV+ individuals identified (testing yield)
- To determine whether group self-testing in waiting areas of OPD and STI clinics is superior in regard to linkage rates for those who identify as HIV-positive compared to standard of care and optimized standard of care (PITC)

2.2. STUDY POPULATION

This aim will be conducted among 15,000 individuals 15 years or older who seek OPD or STI services at participating health facilities. The aim will be conducted in 15 clusters (facilities) in Malawi.

Sites have been selected in collaboration with the Ministry of Health and represent medium to large health facilities in areas of high HIV prevalence. Sites represent a mixture of facility types (hospital versus health centre) and are balanced with regard to the number that have separate STI clinics (versus STI services offered within OPD clinics). Figure 1 outlines potential sites to be included in the study.

FIG 1. STUDY SITES BY FACILITY TYPE, REGION, AND STUDY ARM

Facility Name	Facility Type	Region	Study Arm
Likuni Mission Hospital	CHAM	Central	HIVST
Mponela Rural Hospital	Rural Hospital	Central	HIVST
Nsanje District Hospital	District Hospital	South	HIVST
Masenjere Health Centre	Health Centre	South	HIVST
Mgabu Rural Hospital	Health Centre	South	HIVST
St. Gabriel Mission Hospital	CHAM	Central	OSOC
Kasungu District Hospital	District Hospital	Central	OSOC
Kalulu Health Centre	Rural Hospital	South	OSOC
Sorgini Health Centre	Health Centre	South	OSOC
Kalemba Health Centre	Health Centre	South	OSOC
De Young	CHAM	Central	SOC
Chikwawa District Hospital	District Hospital	South	SOC
Mkumaniza Health Centre	Health Centre	South	SOC
Gaga Health Centre	Health Centre	South	SOC
Chankhungu Health Centre	Health Centre	Central	SOC

2.2.1. Inclusion Criteria

All of the following criteria must be met in order for an individual to be included in Aim 1:

- 15 years of age or older
- Being seen for OPD or STI services at the time of the study

We include children ages 15-18 years of age if they actively seek OPD or STI services and consent to participate in the study. Under Malawian law, children 15-18 are able to receive an HIV test without being accompanied by a parent or receiving parental consent.

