2.2.2. Exclusion Criteria

[figure not shown]
Individuals will be excluded from the study if any of the following exclusion criteria are present:

- Less than 15 years of age
- Not being seen for OPD or STI services at the time of the study
- Guardians attending clinics with OPD or STI clients

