2.4.3. Group Self-Testing Arm

A trained study member will meet with clients waiting in the OPD and STI waiting spaces and read the oral consent script explaining that participation in self-testing and study procedures is voluntary. The HDA will then provide group education in the OPD and STI waiting areas about (1) the benefits of HIV testing and treatment, (2) a demonstration of how to use a self-test kit and who should use the kit for testing, and (3) and group counseling about follow-up needed for both HIV negative (re-testing at regular intervals) and positive results (referral for confirmatory testing and ART initiation and follow-up). All individuals 15 years of age and older in the waiting area will be offered a self-test kit.

Clients who tested HIV negative within the past 3 months, previously tested HIV positive, are currently taking ART, are uncomfortable administering the self-test kit, or would like to receive an assisted HIV test either through standard HIV testing protocols or a provider observed HIV self-test kit will be advised to opt-out from the HIV self-test. Those who would like to opt-out for any reason will be asked to take a kit and give the unopened kit to the research team during a brief exit survey.

Those who would like to take the self-test will perform the test while waiting for their appointment. In order to avoid unintended disclosure to participants sitting in the waiting area, after the sample is obtained, individuals will be instructed to put the kit into the opaque testing bag while waiting for the test results in order to ensure privacy and minimize risk of adverse outcomes due to unintended disclosure (approximately 20 minutes). Participants will be allowed to perform the self-test while seated in the waiting area or may move to a more private location on the facility grounds. A private space (tent or other sectioned off area of the waiting area) will be available for individuals who wish to read their test before entering the provider consultation room. After completing the test, participants may do any of the following:

- Individuals who are willing to share the result with the provider will be asked to bring their kit to the provider for interpretation and counseling.

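### Aim 1's schema and eligibility criteria disagree on known HIV-positive clients, and no listed item records prior status, so re-tests can be counted in yield, linkage and cost per positive identified

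*Combined protocol and SAP*

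**What the plan says.** The schema describes the Aim 1 population as "Individuals 15 years of age and older not already known to be HIV-positive". Section 2.2 describes it differently: "This aim will be conducted among 15,000 individuals 15 years or older who seek OPD or STI services at participating health facilities". The inclusion list in 2.2.1 has two items, age and "Being seen for OPD or STI services at the time of the study". The exclusion list in 2.2.2 covers age under 15, people not attending for these services, and "Guardians attending clinics with OPD or STI clients". Neither list mentions HIV status or ART.

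Section 2.4.3 follows the wider definition: "All individuals 15 years of age and older in the waiting area will be offered a self-test kit". It advises some groups to opt out, among them "Clients who tested HIV negative within the past 3 months, previously tested HIV positive, are currently taking ART". Anyone who opts out is "asked to take a kit and give the unopened kit to the research team during a brief exit survey", and so stays among the people surveyed.

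For every arm, section 2.3.2 takes all OPD and STI attendees aged 15 or over in the registers as the coverage denominator. It defines HIV-positive as positive on both Determine and Uni-Gold and does not require a new diagnosis. The exit-survey items listed in 2.4.1.2, 2.4.2.2 and 2.4.3.4 cover demographics, reason for visit, testing, reasons for testing or not, and self-reported result. Prior HIV status and current ART use are not listed.

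**The concern.** If the schema governs, the criteria admit people whom the trial says it does not study. If the criteria govern, known positives are legitimate participants, but the plan cannot tell a re-test from a new diagnosis.

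Three outcomes are exposed:

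- **Yield:** the secondary objective in 2.1.2 and HIV-positivity among those tested in 2.5.1.
- **Linkage:** under 2.3.3, people who report a positive result that day are tracked for ART, and someone already on ART could appear newly linked.
- **Cost per HIV-positive person identified (2.6, 2.6.2):** this is one of two effectiveness measures behind a primary cost-effectiveness objective.

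The two-test definition does not help, because a known positive would be expected to confirm positive again. The Aim 2 cost sections (6 and 6.2) do specify newly identified positives, so the protocol draws the distinction there but not in Aim 1.

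**Working it through.** **1. The plan's own power figure.** Inputs from 2.5.1: 5 clusters of 1,000 per arm, ICC 0.004, type I error 0.05, coverage 5%, 10% and 60%.

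- Design effect = 1 + 999 × 0.004 = 4.996. Effective n per arm = 5,000 / 4.996 = 1,000.8.
- 5% v 10%: power 98.9% (two-sided, normal), or 96.0% using t with 8 df.
- 10% v 60%: above 99.9%.

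The stated figure of at least 95% reproduces.

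**2. Effect on primary coverage.** Let q be the share of attendees known positive, c the coverage in everyone else, and r the share of known positives who test. Observed coverage = (1 − q)c + qr. The documents give neither q nor r. Assume that the planning figures refer to people not known positive and that r = 0:

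| q | Self-testing | Optimized SOC | Difference (points) | Ratio |
|---|---|---|---|---|
| 5% | 57.0% | 9.5% | 47.5 | 6 |
| 10% | 54.0% | 9.0% | 45.0 | 6 |
| 15% | 51.0% | 8.5% | 42.5 | 6 |

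Power for self-testing v optimized SOC stays above 99.9% throughout. If 10–30% of known positives do test in the self-testing arm, coverage at q = 10% is 55–57% rather than 54%. If q is unequal, say 5% in optimized SOC and 15% in self-testing, the figures are 9.5% and 51.0%, a ratio of 5.4.

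**3. Effect on positives counted in the self-testing arm.** Let u be undiagnosed prevalence among people not known positive (assumed). With 5,000 clients and 60% coverage:

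- New = 5,000 × (1 − q) × u × 0.60
- Re-tests = 5,000 × q × r
- Overstatement = (new + re-tests) / new

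| q | u | r | New | Re-tests | Overstatement | Re-tests as share of positives |
|---|---|---|---|---|---|---|
| 5% | 5% | 10% | 142.5 | 25 | 1.18 | 15% |
| 5% | 5% | 30% | 142.5 | 75 | 1.53 | 34% |
| 5% | 3% | 10% | 85.5 | 25 | 1.29 | 23% |
| 5% | 3% | 30% | 85.5 | 75 | 1.88 | 47% |
| 10% | 5% | 10% | 135 | 50 | 1.37 | 27% |
| 10% | 5% | 30% | 135 | 150 | 2.11 | 53% |
| 10% | 3% | 10% | 81 | 50 | 1.62 | 38% |
| 10% | 3% | 30% | 81 | 150 | 2.85 | 65% |

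For a given total cost, cost per positive is understated by the same factor. Apparent positivity moves too: with q = 10%, u = 5% and r = 10% it is 185 / 2,750 = 6.7% instead of 5%.

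**4. Effect on the comparison between arms.** This depends on how often known positives are re-tested under PITC, which is not given. Take q = 10%, u = 5% and r = 10% in self-testing. Optimized SOC then finds 5,000 × 0.90 × 0.05 × 0.10 = 22.5 new positives, and the true ratio is 135 / 22.5 = 6.

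- No re-tests in optimized SOC: 185 / 22.5 = 8.2.
- Re-testing at the same 10% in optimized SOC: 185 / (22.5 + 50) = 2.6.

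So even the direction of the distortion depends on a rate that the plan does not collect.

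**The case against.** The strongest defence is that the operative text is consistent. Sections 2.2 to 2.4 and the register denominators all use every OPD or STI client aged 15 or over, which is a reasonable pragmatic population. Only one schema line departs from it. Section 2.5.1 does not say that its coverage figures refer to people not known positive; if they refer to all attendees, coverage is not diluted relative to plan. This stands, and it is why the primary comparison is not the problem.

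The yield figures also omit steps. Under 2.4.3 only clients who disclose a positive self-test are referred to an HDA for confirmation, and 2.4.4.1 limits register yield in that arm to routine tests. A known positive enters register-confirmed yield only after disclosing and being re-tested. This stands too: the multiples in the table are upper bounds for their inputs.

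The opt-out advice is a safeguard, and it is documented only in the self-testing arm. Asking why clients did or did not test may reveal some known positives. Neither reliably identifies those who test anyway. Finally, the yield objective speaks of positives identified, not of new ones. That is a fair reading of the wording, but it leaves yield unable to separate case finding from re-testing.

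**Conclusion.** The contradiction between the schema and sections 2.2 to 2.2.2 is real, and nothing elsewhere resolves it. As written, the plan can count re-tests of known positives in HIV-positivity, linkage and cost per HIV-positive person identified. Under the assumed ranges (5–10% known positive, 3–5% new positivity, 10–30% of known positives testing), positives in the self-testing arm are overstated by about 1.2 to 2.9 times as an upper bound. None of these inputs is in the documents.

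A reader might infer two stronger claims:

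- **That the primary coverage result is compromised.** It is not. Power stays above 99.9%, and with r = 0 the ratio stays at 6 if the known-positive share is equal across arms. With five clusters per arm equality is not assured, but a moderate imbalance does not threaten the comparison.
- **That the miscounting falls mainly on the self-testing arm.** This is plausible, since kits are offered to whole waiting rooms while PITC works by individual referral and counselling. But the documents give no rates and do not say that PITC screens out known positives.

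**What to change.** 1. Reconcile the schema population with 2.2, 2.2.1 and 2.2.2. Since all attendees should remain the coverage denominator, the simplest edit is to bring the schema line into agreement with section 2.2.
2. Add a question on prior positive test and current ART use to the exit survey in all three arms, and to the form for those who report a positive result that day.
3. Define yield, linkage and cost per HIV-positive person identified on new diagnoses, and report all positives alongside.
4. Keep all attendees as the primary coverage denominator. Report survey-based coverage among people not known positive as a sensitivity analysis.

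Known positives should not be removed from the primary denominator. Their status would be self-reported after the kit offer, in one arm after advice that known positives should opt out, so reporting could differ by arm. A survey answer also cannot filter anonymized register counts.

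The cost is one added survey item and the related wording, plus self-report error in prior status. The item has to be in place at the visit, because most respondents are anonymous and cannot be asked later.

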2.2.2. Exclusion Criteria

[figure not shown]
Individuals will be excluded from the study if any of the following exclusion criteria are present:

- Less than 15 years of age
- Not being seen for OPD or STI services at the time of the study
- Guardians attending clinics with OPD or STI clients

2.3. STUDY DESIGN

The study design for Aim 1 will be a cluster randomized trial comparing HIV testing rates and cost-effectiveness of group HIV self-testing compared to standard of care and optimized standard of care among OPD and STI clients (see Fig. 2). Clusters will be comprised of individual facilities in Malawi. Individuals waiting to receive OPD and STI health services who meet the inclusion criteria will be asked to participate in the study.

FIG 2. OVERVIEW OF STUDY DESIGN

